## 10 GLOSSARY OF TERMS

Term	Definition
Adverse Reaction	An adverse event that is considered by either the investigator or BMS as related to the investigational product
Unexpected Adverse Reaction	An adverse reaction, the nature or severity of which is not consistent with the applicable product information (eg, Investigator Brochure for an unapproved investigational product)
Serious Adverse Event	Serious adverse event defined as any untoward medical occurrence that at any dose: results in death; is life threatening (defined as an event in which the subject was at risk of death at the time of the event; it does not refer to an event which hypothetically might have caused death if it were more severe), requires inpatient hospitalization or causes prolongation of existing hospitalization; results in persistent or significant disability/incapacity, is a congenital anomaly/birth defect; is an important medical event (defined as a medical event(s) that may not be immediately life threatening or result in death or hospitalization but, based upon appropriate medical and scientific judgment, may jeopardize the subject or may require intervention [eg, medical, surgical] to prevent one of the other serious outcomes listed in the definition above). Examples of such events include, but are not limited to, intensive treatment in an emergency room or at home for allergic bronchospasm; blood dyscrasias or convulsions that do not result in hospitalization.). For reporting purposes only, BMS also considers the occurrence of pregnancy, overdose (regardless of association with an AE), and cancer as important medical events.

## 11 LIST OF ABBREVIATIONS

Term	Definition
ADA	anti-drug antibody
AE	adverse event
ALM	Acral lentiginous melanoma
ALP	alkaline phosphatase
ALT	alanine aminotransferase
ANC	absolute neutrophil count
APC	antigen presenting cells
AST	aspartate aminotransferase
BA/BE	bioavailability/bioequivalence
BLA	Biologic License Agreement
BMS	Bristol-Myers Squibb
BOR	best overall response
BORR	best overall response rate
BP	blood pressure
BSA	body surface area
BUN	blood urea nitrogen
C	Celsius
CBC	complete blood count
CDE	Center for Drug Evaluation
CFR	Code of Federal Regulations
CI	confidence interval
CL	clearance
CMH	Cochran-Mantel-Haenszel
CR	complete response
CRF	Case Report Form, paper or electronic
CRP	C-reactive protein
CT	computed tomography
CTA	clinical trial agreement
CTCAE	Common Terminology Criteria for Adverse Events

Term	Definition
CTLA-4	cytotoxic T-lymphocyte-associated antigen 4
DC	dendritic cells
DCR	disease control rate
dL	deciliter
DTIC	Dacarbazine
ECG	electrocardiogram
ECOG	Eastern Cooperative Oncology Group
eCRF	Electronic Case Report Form
EDC	Electronic Data Capture
eg	exempli gratia (for example)
EORTC QLQ-C30	European Organisation for Research and Treatment of Cancer Quality of Life Questionnaire
EQ-5D	European Quality of Life-5 Dimensions
E-R	exposure-response
EU	European Union
FDA	Food and Drug Administration
FSH	follicle stimulating hormone
GCP	Good Clinical Practice
GI	gastrointestinal
HBsAg	hepatitis B surface antigen
HBV	hepatitis B virus
HCV	hepatitis C virus
HIV	Human Immunodeficiency Virus
HR	hazard ratio
HRQoL	Health Related Quality of Life
IBW	ideal body weight
ICF	informed consent form
ICH	International Conference on Harmonisation
ie	id est (that is)
IEC	Independent Ethics Committee
IL/U	international units

Term	Definition
imAR	immune-mediated adverse reaction
IMP	investigational medicinal products
IND	Investigational New Drug Exemption
irAEs	Immune-related AEs
IRB	Institutional Review Board
IV	intravenous
IVRS	interactive voice response system
kg	kilogram
LDH	lactate dehydrogenase
MHC	major histocompatibility complex
mg	milligram
MCM	mucosal melanoma
mm	millimeter
MRI	magnetic resonance imaging
n	number, count
N/A	not applicable
NCI	National Cancer Institute
NIMP	non-investigational medicinal products
NM	nodular melanoma
Non-CR	Non complete response
Non-PR	Non partial response
NSAID	nonsteroidal anti-inflammatory drug
ORR	objective response rate
OS	overall survival
PD	progressive disease
PFS	Progression Free Survival
PK	pharmacokinetics
RBC	red blood cell
SAE	serious adverse event
SAP	statistical analysis plan

Term	Definition
SD	stable disease
SEER	Surveillance Epidemiology and End Result
SFDA	State Food and Drug Administration
SOP	Standard Operating Procedures
SSM	superficial spread melanoma
TA	tumor assessment
TCR	T cell-receptor
TMZ	Temozolomide
TSH	thyroid stimulating hormone
ULN	upper limit of normal
US	United States
US NCCN	US National Comprehensive Cancer Network
VAS	visual analog scale
Vd	volume of distribution
WBC	white blood cell
WHO	World Health Organization
WOCBP	women of childbearing potential

## APPENDIX 1 ECOG PERFORMANCE STATUS

ECOG PERFORMANCE STATUS	
Grade	ECOG
0	Fully active, able to carry on all pre-disease performance without restriction
1	Restricted in physically strenuous activity but ambulatory and able to carry out work of a light or sedentary nature, eg, light house work, office work
2	Ambulatory and capable of all self-care but unable to carry out any work activities. Up and about more than 50% of waking hours.
3	Capable of only limited self-care, confined to bed or chair more than 50% of waking hours
4	Completely disabled. Cannot carry on any self-care. Totally confined to bed or chair
5	Dead

Source: Oken MM, Creech RH, Tormey DC, Horton J, Davis TE, McFadden ET, and Carbone PP. Toxicity and Response Criteria of the Eastern Cooperative Oncology Group. Am J Clin Oncol 1982;5:649-655.

9. Have you had pain?	1	2	3	4
10. Did you need to rest?	1	2	3	4
11. Have you had trouble sleeping?	1	2	3	4
12. Have you felt weak?	1	2	3	4
13. Have you lacked appetite?	1	2	3	4
14. Have you felt nauseated?	1	2	3	4
15. Have you vomited?	1	2	3	4
16. Have you been constipated?	1	2	3	4
17. Have you had diarrhea?	1	2	3	4
18. Were you tired?	1	2	3	4

**DURING THE PAST WEEK:**

	NOT AT ALL	A LITTLE	QUITE A BIT	VERY MUCH
19. Did pain interfere with your daily activities?	1	2	3	4
20. Have you had difficulty in concentrating on things, like reading a newspaper or watching television?	1	2	3	4
21. Did you feel tense?	1	2	3	4
22. Did you worry?	1	2	3	4
23. Did you feel irritable?	1	2	3	4
24. Did you feel depressed?	1	2	3	4
25. Have you had difficulty remembering things?	1	2	3	4
26. Has your physical condition or medical treatment interfered with your family life?	1	2	3	4
27. Has your physical condition or medical treatment interfered with your social activities?	1	2	3	4
28. Has your physical condition or medical treatment caused you financial difficulties?	1	2	3	4

For the following questions please circle the number between 1 and 7 that best applies to you

29. How would you rate your overall health during the past week?

1      2      3      4      5      6      7

Very poor

Excellent

30. How would you rate your overall quality of life during the past week?

1      2      3      4      5      6      7

Very poor

Excellent

## APPENDIX 3 EQ-5D HEALTH QUESTIONNAIRE

Health Questionnaire  
English version for the UK (validated for Ireland)

**By placing a tick in one box in each group below, please indicate which statements best describe your own health state today.**

### 1) Mobility

- I have no problems in walking about
- I have some problems in walking about
- I am confined to bed

### 2) Self-Care

- I have no problems with self-care
- I have some problems washing or dressing myself
- I am unable to wash or dress myself

### 3) Usual Activities (e.g. work, study, housework, family or leisure activities)

- I have no problems with performing my usual activities
- I have some problems with performing my usual activities
- I am unable to perform my usual activities

### 4) Pain/Discomfort

- I have no pain or discomfort
- I have moderate pain or discomfort
- I have extreme pain or discomfort

### 5) Anxiety/Depression

- I am not anxious or depressed
- I am moderately anxious or depressed
- I am extremely anxious or depressed

[figure not shown]
©1998 EuroQol Group. EQ-5D™ is a trade mark of the EuroQol Group

To help people say how good or bad a health state is, we have drawn a scale (rather like a thermometer) on which the best state you can imagine is marked 100 and the worst state you can imagine is marked 0.

We would like you to indicate on this scale how good or bad your own health is today, in your opinion. Please do this by drawing a line from the box below to whichever point on the scale indicates how good or bad your health state is today.

**Your own  
health state  
today**

Best  
imaginable  
health state

Worst  
imaginable  
health state

## 2 STUDY DESCRIPTION

### 2.1 Study Design

This SAP addresses the randomized, open-label study, CA184248, for which the planned sample size is approximately 180 randomized subjects with 2:1 allocation to ipilimumab 3mg/kg or DTIC.

An overview of the administration of study drug and assessment schedule is presented in Figure 2.1-1. Further details of the design are given in the Protocol.

**Figure 2.1-1: Study Design Schematic**

### 2.2 Treatment Assignment

After informed consent has been obtained, the site will enroll a subject into the study at the time of eligibility screening by accessing a call-in Interactive Voice Response System (IVRS). A subject number will be assigned by the IVRS at this time.

Following completion of all Screening evaluations, all eligible subjects will be randomized to one of two arms in a 2:1 ratio (Ipilimumab:DTIC) using a stratified permuted block randomization method with the following stratification actors:

- M-substage (M1a+M1b vs. M1c);
- BRAF mutation status (yes vs. no).

### **2.3 Blinding and Unblinding**

Not applicable (open-label study).

### **2.4 Protocol Amendments**

This SAP reflects the protocol amendments described in Table 2.4-1:

**Table 2.4-1: Protocol Amendments**

Amendments	Date of Issue	Summary of Major Changes
Revised Protocol 1	08-JUL-2015	

- Update the dose of DTIC per China label requirement.

- Other changes per program level standards and model document.

Revised Protocol 2	23-DEC-2015	

- Remove the use of a Data Monitoring Committee (DMC since:

1) This is an open-label study;

2) This is a single country study (China) and not a MRCT (Multi Regional Clinical Trial) and therefore an independent DMC is not required as per the Chinese regulation.

- Further clarification with regards to:

1) The infusion pump used for the administration of ipilimumab;

2) The T&E schedule (Endocrine assessments and collection of PK/ADA)

Revised Protocol 3	20-DEC-2018	

-Change in primary objective and primary endpoint to 2-year OS rate from OS

-Change in allowable minimum scan time from baseline for determination of stable disease from 12 weeks to 8 weeks per RECIST v1.1 guidelines

## **3 OBJECTIVES**

### **3.1 Primary**

- To compare the survival rate at 2 years in chemotherapy naive Chinese subjects with Stage IV melanoma who have been randomized to ipilimumab (3mg/kg) vs. DTIC (250mg/m^2 - Day 1 - 5).

### **3.2 Secondary**

- To estimate survival rates at 1 year for each treatment arm;
- To compare overall survival between the two arms
- To compare PFS between the two arms by RECIST v1.1;
- To compare disease control rate between the two arms by RECIST v1.1;

- To estimate best overall response rate, duration of response, and duration of stable disease for each treatment arm by RECIST v1.1.

## **4 ENDPOINTS**

### **4.1 Primary Endpoint**

#### **4.1.1 Two-Year Survival Rate**

Two-year survival rate is defined as the probability that a subject is alive at 2 years following the randomization date and will be estimated via the Kaplan-Meier (KM) method.

### **4.2 Secondary Endpoints**

Secondary response-based endpoints of PFS, DCR, DoR, DoSD, and BORR will be captured using the RECIST v1.1 criteria.

#### **4.2.1 One-Year Survival Rate**

Survival rate at 1 year is defined as the probability that a subject is alive at 1 year following the randomization date and will be estimated via the Kaplan-Meier (KM) method.

#### **4.2.2 Overall Survival**

OS is defined for each subject as the time between randomization date and the date of death (of any cause). If a subject has not died, the subject will be censored at the time of last contact (last known alive date).

A modified variable will be examined for the purposes of sensitivity analysis:

- OS accounting for subsequent PD-1/PD-L1 therapy will be defined through addition of the following restriction to the primary definition: subjects who receive subsequent PD-1/PD-L1 cancer therapy will be censored at the start date of subsequent PD-1/PD-L1 therapy.

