## 5 SAMPLE SIZE AND POWER

Approximately 180 Chinese subjects will be randomized to ipilimumab and DTIC at a 2:1 ratio and followed at least 2 years after randomization to ensure 80% power through simulation using a chi-squared test with a Type I error rate of 0.20 to reject the null hypothesis of no difference in 2-year survival rate between treatment groups, assuming a HR [ipilimumab vs DTIC] of 0.67. Under an exponential distribution, this hazard ratio (HR) would correspond to an 12 month median OS for the ipilimumab arm with an 8 month median OS in the DTIC arm^8(or equivalently 25% and 12.5% in the ipilimumab and DTIC arm). The accrual duration is approximately 18 months, assuming a monthly rate of 10 subjects per month. The primary analysis will be performed about 42 months after the first subject is randomized.

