## 7 STATISTICAL ANALYSES

### 7.1 General Methods

No interim analyses are planned for this study. The final analysis will be performed when a minimum of 2 year follow-up is reached by all randomized subjects.

Unless otherwise noted, the bulleted titles in the following subsections describe tabulations of discrete variables, by the frequency and proportion of subjects falling into each category, grouped by treatment (with total). Percentages given in these tables will be rounded to the first decimal and, therefore, may not always sum to 100%. Percentages less than 0.1 will be indicated as ‘< 0.1’. Continuous variables will be summarized by treatment group (with total) using the mean, standard deviation, median, minimum and maximum values. Subject listings will be produced to accompany the tabulations. Time-to-event variables (e.g. time-to resolution) will be analyzed using the Kaplan-Meier technique. When specified, the median will be reported along with 80% CI using Brookmeyer and Crowley method (using log-log transformation for constructing the confidence intervals). The conventions to be used for imputing partial dates for analyses requiring dates are described in [Section 8](#).

Frequency tables of subject characteristics and subset analyses of efficacy endpoints (including those by M-substage and BRAF mutation status) will be based on the assessment recorded on the baseline CRF. However, stratified analyses will be based on the variables used by the IVRS to randomize the subject.

Assessments taken during re-induction and subsequent progression follow-up phase will not contribute to derived endpoints, such as BOR or PFS, since these assessments are necessarily following an initial progression. However exploratory version of these endpoints corresponding to the administration of re-induction therapy may be performed (if there are sufficient data) - details will be provided in the DPP.

All statistical analyses will be carried out using SAS software (SAS Institute, Cary, North Carolina, USA), unless otherwise noted.

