### **7.5.1 Survival Rates at Specified Time Points**

Yearly survival rates will be calculated for each treatment group using the KM product-limit method, along with their corresponding log-log transformed 80% CIs.

Two-year survival rate is the primary endpoint. The survival rate at 2 years will be compared between treatment group using a chi-square test stratified by M substage (M1a+M1b versus M1c) and BRAF mutation status (yes vs no), as recorded in the IVRS. The stratified chi-square test is defined by the following formula:

$$\chi^2 = \frac{\left( \sum_{s=1}^m \hat{S}_{1s}(t) - \hat{S}_{2s}(t) \right)^2}{\sum_{s=1}^m \hat{V}(\hat{S}_{1s}(t)) + \hat{V}(\hat{S}_{2s}(t))},$$

where  $\hat{S}_{ks}(t)$  and  $\hat{V}(\hat{S}_{ks}(t))$  be the Kaplan-Meier estimate and variance based on the Greenwood formula for the  $s$ th stratum in the  $k$ th treatment group at time  $t$ .

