#### **7.5.1.1 Subgroup Analyses**

Two-year survival rates along with two-sided 80% CI based on the log-log transformation will be presented within subsets defined by information recorded on the baseline CRF.

This summary and comparison based on the unstratified chi-square test will be provided for the following subgroups:

- by age (< 65,  $\geq$  65)
- by gender (male, female)
- by M-Substage at study entry (M1a/M1b, M1c)
- by ECOG performance status (0, 1)

- by baseline LDH ( $\leq$ ULN,  $>$  ULN)
- by baseline LDH ( $\leq 2 \times$  ULN,  $> 2 \times$ ULN)
- by BRAF mutation status (positive, negative, unknown)
- by subtype (acral, cutaneous, other)

In case a subgroup includes less than 10 subjects, the analysis for the given subgroup will not be carried out (or the possibility of combining subgroups will be considered).

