### **7.5.1.2 Sensitivity Analyses**

The following analyses will be conducted

- An unstratified chi-square test will be performed to compare survival rate at 2 years after randomization between treatment groups
- The stratified and unstratified chi-square tests based on the modified OS accounting for subsequent PD-1/PD-L1 therapy.

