#### **For date of last tumor assessment:**

- If only the day of the month is missing, the 1st of the month will be used to replace the missing day(\*)).

- If the day and month are missing or a date is completely missing, it will be considered as missing.

(\*) In case the date of death is present (complete date), the imputed date will be compared with the date of death. The minimum of the (imputed date, date of death) will be considered as the date of last tumor assessment.

Otherwise, missing values will not in general be imputed. Regardless of missing data, all subjects will contribute to the calculation of the following tumor response endpoints (as detailed in [Sections 4.2.3-4.2.6](#)): BORR and disease control rate (by inclusion in the denominators); and in the Kaplan-Meier analyses (by censoring, as appropriate) of DoR (for subjects with confirmed CR or PR), DoSD (for subjects whose BOR is SD) and PFS.

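### Does the stratified 2-year test on OS censored at PD-1/PD-L1 therapy need a written rule for strata with no 24-month estimate?

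*SAP*

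**What the plan says.** SAP Section 4.2.2 defines, for sensitivity analysis only, a modified OS in which "subjects who receive subsequent PD-1/PD-L1 cancer therapy will be censored at the start date of subsequent PD-1/PD-L1 therapy". Section 7.5.1.2 then plans "The stratified and unstratified chi-square tests based on the modified OS accounting for subsequent PD-1/PD-L1 therapy".

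Section 7.5.1 introduces the statistic with the words "The stratified chi-square test is defined by the following formula". It sums over strata the difference between the arms' Kaplan-Meier estimates at time t, squares the sum, and divides by the summed Greenwood variances. The strata are M-substage (two levels) by BRAF status (two levels), and Section 2.2 says "all eligible subjects will be randomized to one of two arms in a 2:1 ratio".

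For unmodified OS, Section 5 has subjects "followed at least 2 years after randomization", and Section 7.1 adds: "The final analysis will be performed when a minimum of 2 year follow-up is reached by all randomized subjects".

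Two other rules come near the point. Section 7.5.1.1 says "In case a subgroup includes less than 10 subjects, the analysis for the given subgroup will not be carried out". Section 8 says "Otherwise, missing values will not in general be imputed". Section 8 also leaves further conventions to the Data Presentation Plan, which is not among the documents.

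**The concern.** Two years of minimum follow-up protects the unmodified OS: no one is administratively censored before 24 months, so with complete follow-up no cell's curve stops short in a censoring. Censoring at the start of PD-1/PD-L1 therapy removes that protection. If the last subject under observation in one of the 8 cells is censored before 24 months, the cell has no 2-year estimate and the sum has no value.

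Neither nearby rule covers this. The 10-subject rule concerns subgroups and counts subjects, not subjects still at risk. The sentence on missing values closes the date-imputation conventions and leads into tumor response endpoints; it does not address a Kaplan-Meier value that cannot be estimated.

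An analyst could therefore carry the last estimate forward, set it to zero or drop the stratum, after seeing open-label data. At stake is whether a planned check of the primary endpoint against later immunotherapy has a result that does not depend on that choice.

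**Working it through.** **1. The plan's own figure.** Inputs from SAP Sections 5 and 7.5: 180 subjects at 2:1 (120 and 60), 2-year rates 25% and 12.5%, two-sided level 0.20. With unpooled variance, the form of the SAP statistic:

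- variance = 0.25 × 0.75/120 + 0.125 × 0.875/60 = 0.001563 + 0.001823 = 0.003385, so the standard error is 0.0582
- 0.125/0.0582 = 2.148, and power = Φ(2.148 − 1.282) = Φ(0.867) = 80.7%

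This reproduces the stated 80%.

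**2. How thin the cells are.** 2 × 2 strata × 2 arms = 8 cells. Expected DTIC survivors at 24 months: 60 × 0.125 = 7.5, or 1.9 per stratum if strata were equal. For ipilimumab: 120 × 0.25 = 30, or 7.5 per stratum. A few censorings can empty a DTIC cell.

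**3. When a cell is undefined.** Having nobody at risk at 24 months is not enough; the last observation must be a censoring. If it is a death, the estimate is 0, but the last Greenwood term divides by zero and the variance needs a convention, usually 0. That situation needs no switching and affects the primary stratified test too. With four equal DTIC strata of 15, the chance of no 2-year survivor in one stratum is 0.875^15 = 0.135, and in at least one it is 1 − (1 − 0.135)^4 = 0.44. Saying that the test is always defined without switching therefore already assumes the zero-variance convention.

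**4. How often switching makes the stratified test undefined.** The documents give no uptake, timing or stratum shares, so all are assumed. The first model uses exponential OS with medians 12 and 8 months, follow-up of 24 to 42 months, permuted blocks of 3 within stratum, M1c 50%, PD-1/PD-L1 start uniform over months 3 to 18, and 2,000 runs per setting. Columns give the share of subjects actually censored at the switch.

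| N | BRAF-positive | 5% | 10% | 21% | 31% |
|---|---|---|---|---|---|
| 180 | 15% | 7% | 16% | 37% | 66% |
| 180 | 25% | 3% | 9% | 25% | 57% |
| 180 | 50% | 1% | 3% | 17% | 45% |
| 258 | 15% | 4% | 11% | 26% | 55% |
| 258 | 25% | 1.5% | 5% | 16% | 42% |
| 258 | 50% | 0.7% | 1.3% | 7% | 28% |

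The value 258 is the number enrolled in Protocol Section 3.1; the number randomized is not stated.

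A second model has progression followed by death, and uptake set separately by arm (ipilimumab/DTIC). With switching independent of prognosis and N = 180 it gives 11–22% at 10%/10%, 30–40% at 10%/20% and 54–63% at 10%/30%. With switching only after progression it gives 39–53% at 10%/20% and 60–74% at 10%/30%. Another run with its own assumed uptake and strata gives 6%, 17% and 32% at 10%/10%, 10%/20% and 10%/30%. The same nominal uptake thus gives answers that differ about twofold or more.

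**5. The test planned beside it.** The unstratified test on the modified OS is undefined in at most 0.25% of runs in the first model and 0–2% in the second with independent switching. A further simulation with independent switching gave up to about 3%. The maximum in any setting is 9%. Collapsing to M-substage alone leaves 0–8% undefined in the first model.

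**The case for a change.** The best case for a change is that the handling choice matters when it arises. In the second model (central stratum mix, independent switching), the decision at 0.20 differed between carrying forward, setting to zero and dropping the stratum in 24–44% of the undefined trials. Under a true null, stratified rejection at 10%/20% and 10%/30% uptake was 0.29–0.34 and 0.31–0.41 depending on the choice, against 0.22 and 0.23 unstratified. Removing the stratified test would cost little and would end the ambiguity.

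What stands is that the SAP leaves the cell rule unwritten and that the three ad hoc choices are not equivalent. The conclusion drawn from it does not follow, for four reasons:

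- No decision attaches to this test, so a changed verdict at 0.20 in a sensitivity analysis changes nothing the trial concludes.
- Part of the stratified inflation comes from sparse cells and exists without switching (0.23 in one model and 0.25 in another, against nominal 0.20).
- Nothing in the documents supports higher uptake on DTIC, yet the largest figures assume it.
- Deleting a prespecified test after the 03Jun2019 database lock of an open-label trial would itself be post hoc. Statisticians would differ between deleting it, collapsing strata and falling back on the unstratified version.

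Dependent censoring is a fair caution, but it is not specific to this test. The unstratified test and the modified-OS analyses in Section 7.5.2.3 also censor at the switch and share the assumption. That is the ordinary limit of such an analysis.

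**Conclusion.** The gap is genuine but minor, and analysts fill it sensibly. If a cell has no estimate at 24 months, the stratified result for the modified OS is not estimable, and the unstratified test already planned in the same bullet answers the question. The modified-OS comparison in Section 7.5.2.3 also remains. It needs no 24-month estimate if it follows the log-rank and Cox methods of Section 7.5.2.1. The Data Presentation Plan may already hold the convention.

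The documents support the possibility of an undefined test, not a frequency. The simulated range with switching, from under 1% to 74%, reflects assumed uptake, timing, stratum mix and sample size. The unstratified alternative fails in at most about 3% of trials if switching is independent of prognosis, and in at most 9% in any setting examined. The primary 2-year test and the main OS analysis do not censor at the switch. The zero-variance convention for cells ending in a death is a separate programming detail that the primary stratified test shares. The trial's conclusions stay sound if the plan is followed as written, so no change follows.
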